10.4.3 Recording and Follow-up of AE and SAE

AE and SAE Recording

When an AE/SAE occurs, it is the responsibility of the Investigator to review all documentation (e.g., hospital progress notes, laboratory, and diagnostics reports) related to the event.The Investigator will then record all relevant AE/SAE information in the CRF.It is not acceptable for the Investigator to send photocopies of the participant's medical records to the clinical research organization (CRO) in lieu of completion of the AE/SAE CRF page.There may be instances when copies of medical records for certain cases are requested by the CRO. In this case, all participant identifiers, with the exception of the participant number, will be blinded on the copies of the medical records before submission to Parexel Safety Services for review.The Investigator will attempt to establish a diagnosis of the event based on signs, symptoms, and/or other clinical information. In such cases, the diagnosis (not the individual signs/symptoms) will be documented as the AE/SAE.
Assessment of Intensity

The Investigator will make an assessment of intensity for each AE and SAE reported during the study and assign it to one of the following categories:
 
Mild: An event that is easily tolerated by the participant, causing minimal discomfort and not interfering with everyday activities.Moderate: An event that causes sufficient discomfort and interferes with normal everyday activities.Severe: An event that prevents normal everyday activities. An AE that is assessed as severe should not be confused with an SAE. Severe is a category utilized for rating the intensity of an event; and both AE and SAE can be assessed as severe. 
An event is defined as 'serious' when it meets at least one of the predefined outcomes as described in the definition of an SAE, NOT when it is rated as severe.

Assessment of Causality

- The Investigator is obligated to assess the relationship between study intervention and each occurrence of each AE/SAE.
- A "reasonable possibility" of a relationship conveys that there are facts, evidence, and/or arguments to suggest a causal relationship, rather than a relationship cannot be ruled out.
- The Investigator will use clinical judgment to determine the relationship.
- Alternative causes, such as underlying disease(s), concomitant therapy, and other risk factors, as well as the temporal relationship of the event to study intervention administration will be considered and investigated.
- The Investigator will also consult the Investigator's Brochure and/or Product Information, for marketed products, in his/her assessment.
- For each AE/SAE, the Investigator **must** document in the medical notes that he/she has reviewed the AE/SAE and has provided an assessment of causality.
- There may be situations in which an SAE has occurred, and the Investigator has minimal information to include in the initial report in the electronic CRF/EDC. However, **it is very important that the Investigator always make an assessment of causality for every event before the initial transmission of the SAE data to electronic CRF/EDC.**
- The Investigator may change his/her opinion of causality in light of follow-up information and send an SAE follow-up report with the updated causality assessment.
- The causality assessment is one of the criteria used when determining regulatory reporting requirements.

Follow-up of AE and SAE

- The Investigator is obligated to perform or arrange for the conduct of supplemental measurements and/or evaluations as medically indicated or as requested by the DMC to elucidate the nature and/or causality of the AE or SAE as fully as possible. This may include additional laboratory tests or investigations, histopathological examinations, or consultation with other health care professionals.
- New or updated information will be recorded in the originally completed CRF.

- The Investigator will submit any updated SAE data to the Sponsor within 24 hours of receipt of the information.

10.4.4 Reporting of SAE

SAE Reporting to Parexel Safety Services via Electronic Data Collection Tool

The Investigator must report any SAEs to the Parexel Safety Services within 24 hours of becoming aware of the event.

All SAEs will be recorded from signing of informed consent until the end of the study. Serious adverse events occurring after the end of the study and coming to the attention of the Investigator must be reported only if they are considered (in the opinion of the Investigator) causally related to study intervention.

- The primary mechanism for reporting an SAE to Parexel Safety Services will be the electronic data collection tool.
- The site will additionally use the paper SAE data collection tool.
- If the electronic system is unavailable, then the site will use the paper SAE data collection tool in order to report the event within 24 hours.
- The site will enter the SAE data into the electronic system as soon as it becomes available.
- The Investigator and the Sponsor (or Sponsor's designated agent) will review each SAE report and the Sponsor/Parexel will evaluate the seriousness and the causal relationship of the event to study intervention. In addition, the Sponsor (or Sponsor's designated agent) will evaluate the expectedness according to the reference document (Investigator Brochure or Summary of Product Characteristics). Based on the Investigator and Sponsor's assessment of the event, a decision will be made concerning the need for further action.
- After the study is completed at a given site, the electronic data collection tool will be taken off-line to prevent the entry of new data or changes to existing data.
- If a site receives a report of a new SAE from a study participant or receives updated data on a previously reported SAE after the electronic data collection tool has been taken off-line, then the site can report this information on a paper SAE form (see next section) or to the Medical Monitor by email.
- Contacts for SAE reporting can be found in the Investigator Manual.

Suspected Unexpected Serious Adverse Reactions (SUSARs)

Any AE that is a SUSAR has additional reporting requirements, as described below.

- If the SUSAR is fatal or life-threatening, associated with study intervention, and unexpected, regulatory authorities and IECs will be notified within seven calendar days after the Sponsor learns of the event. Additional follow-up (cause of death, autopsy report, and hospital report) information should be reported within an additional 8 days (15 days total).
- If the SUSAR is not fatal or life-threatening but is otherwise serious, associated with study intervention, and unexpected, regulatory authorities and IECs will be notified within 15 calendar days after the Sponsor learns of the event.

The Sponsor will notify the Investigators in a timely fashion of relevant information about SUSARs that could adversely affect the safety of participants. Follow-up information may be submitted if necessary.

The Sponsor will also provide annual safety updates to the regulatory authorities and IECs responsible for the study. These updates will include information on SUSARs and other relevant safety findings.

All SAEs that occur during the study, and all SAEs occurring up to 18 days after receiving the last dose of study intervention, whether considered to be associated with the study intervention or not, must be reported within 24 hours via electronic data collection tool and paper data collection tool to Parexel Safety Services.

The minimum information required for an initial report is:

Name of person sending the report (e.g., name, address of Investigator);

- Participant identification (screening/randomization number, initials, NOT participant name);
- Protocol number;
- Description of SAE;
- Causality assessment, if possible.

However, as far as possible all points on the SAE form should be covered in the initial report, or the completed SAE form itself must be emailed or faxed to the Parexel Safety Services. In addition, the event must be documented in the electronic CRF/EDC system.

After receipt of the initial report, Parexel Safety Services will review the information and, if necessary, contact the Investigator, to obtain further information for assessment of the event. Parexel will be responsible for all information processing and reporting according to local legal requirements. Where necessary, Investigators will inform regulatory authorities in their own countries.

10.5 Appendix 5: Statistical Design Considerations

10.5.1 Some General Design Considerations

1. Binary primary endpoint: progression to critical stage/death up to Day 14
 - to be analyzed by a Cochran-Mantel-Haenszel (CMH) stratified for the factors used in the stratified randomization
 - subjects who withdraw from study treatment will be followed up until their primary endpoint outcome is known (i.e., up to Day 14 or progression to critical stage/death, whatever is first)
 - it is, therefore, not clear what current protocol synopsis text could mean: *If subjects are discharged from the hospital prior to day 14 due to improvement of the clinical status and their status on day 14 cannot be obtained, their status on day 14 for the primary endpoint will be imputed with the status on the day of discharge. and what the implications on statistical study characteristics could be. Further discussion is needed.*
2. Timing of the two planned interim analyses with stopping options is stated as

There are 2 interim analyses planned, the first interim analysis after the first 60 participants have completed day 10 of the observation period ... and a second interim analysis after 150 participants have completed day 14 of the observation period.

With the current text for the timing of the first interim analysis, it is not clear how many subjects will have been randomized at least 14 days prior to the interim data cut-off date and can therefore provide data for the binary primary endpoint (“progression to critical stage/death up to Day 14”).

For such a binary endpoint, Parexel does not recommend including any participant randomized less than 14 days prior to the interim data cut-off date (note this would be different to a study with a time-to-event endpoint) as

- for such participants not yet progressed, the outcome up to Day 14 is unknown and should not be imputed as “not progressed up to Day 14”
- for such participants progressed prior to Day 14, the outcome is known but their inclusion would bias the estimation of progression probability up to Day 14 in a upwards direction.

In order to set up the adaptive group-sequential study design, the following assumptions have been used:

- first interim analysis: a total of ≈ 39 participants randomized at least 14 days prior to data cut-off date
- second interim analysis: a total of $\approx 50\%$ of the initially planned number of participants randomized at least 14 days prior to data cut-off date.

3. Non-binding DMC guidance for stopping the study for futility at the first interim analysis is stated as:

If the difference in the percentage of participants with at least a 2% improvement in SpO₂ between both treatment arms is less than 5%, a benefit of RESP301 treatment is not expected. For a final decision to stop the study for futility the results on other endpoints will be considered as well.

As the main futility stopping criterion is based on improvement in SpO₂ (and not on the primary efficacy endpoint), this first interim analysis will be “ignored” in these statistical considerations for an adaptive group-sequential design. We may revisit the first interim analysis at a later point in time when more information is available.

4. Non-binding DMC guidance for stopping the study for futility at the second interim analysis stated as:

The futility criterion for the second interim analysis will be based on the conditional power (CP) for the final results based on the assumption that the remainder of the study will follow the same trend as observed in the interim analysis. If CP at the time of the second interim analysis is less than 20% consideration will be given to stop the study for futility.

5. Current DMC guidance for stopping the study for superior efficacy at the second interim analysis is stated as:

To account for the multiple testing due to the second interim analysis an adjustment for the type-I-error probability will be applied using the Haybittle-Peto approach with one sided alpha=0.0005 at the second interim analysis and leave one-sided nominal alpha of 0.0249 for the final analysis.

6. For initial sample size calculation, the following additional assumptions / features from the protocol have been used

- progression probability up to Day 14 for Standard of Care (SOC): 30%

- progression probability up to Day 14 for RESP301+SOC: 15%
- desired power assuming the alternative hypothesis stated above: 80%
- 2:1 randomization

7. Method for adaptation of the sample size based on the second interim analysis data is stated as

A sample size re-estimation will be performed to achieve 80% conditional power at the end of the study. The methodology for the adjustment and the procedure to maintain the type-I-error level will be described in greater detail in an appendix to the protocol. The maximum increase of the sample size will be limited to a total number of 600 randomized subjects.

Parexel has put a suggestions with some fictitious interim data for illustration in Section 10.5.3; that section also illustrates by simulations the Cui/Hung/Wang (CWH) approach using a weighted (weights fixed at the design-stage) test for the final analysis versus the Chen/DeMets/Lan (CDL) approach without such weights at the final analysis.

10.5.2 General Design Characteristics

Parexel proposes to base non-binding futility stopping criteria on conditional power criteria. Conditional power (CP) is the conditional probability for achieving statistically significant superiority of RESP301+SOC over SOC at the final analysis, given the interim results and calculated by assuming the interim estimates to be the true distribution parameters for the remaining part of the study (an alternative would be predictive power (PP), a Bayesian version of CP where prior distributions and observed interim results are combined to obtain the probability for achieving statistically significant superiority of gimsilumab over placebo at the final analysis).

Randomization 2:1	Group-Sequential Design
1 st Interim Analysis (IA)	$N \approx 39$ for D14 $\approx 50\%$ for D14
Futility criterion 1 st IA	Based on SpO ₂
Futility criterion 2 nd IA	CP < 4%
Superior efficacy criterion 2 nd IA	p < 0.0005
Total sample size required for 80% power	300
Futility stopping probability at 2 nd IA under “No effect”	1 st IA: NA 2 nd IA: 70%
Futility stopping probability at 2 nd IA under “Planned effect 30% vs 15%”	1 st IA: NA 2 nd IA: 6%
Superiority stopping probability at 2 nd IA under “Planned effect 30% vs 15%”	10%
Superiority stopping probability at 2 nd IA under “30% vs 10%”	28%

10.5.3 Adaptive Sample Size Re-Estimation

Another objective of the 2nd interim analysis is to re-estimate the sample size based on the unblinded interim results.

Proposed procedure at 2nd interim analysis (planned to include approximately 150 subjects)

- unblinded analysis of the primary efficacy endpoint (“progression to level >4 of modified WHO ordinal COVID-19 scale by Day 14” as a binary endpoint)
- calculation of conditional power (CP) given the interim results and calculated by assuming the interim estimates to be the true distribution parameters for the remaining part of the study
 - if $CP < 4\%$: recommend early stop for futility
 - if one-sided p-value < 0.0005 : recommend early stop for superior efficacy
 - if $50\% < CP < 80\%$ and one-sided p-value ≥ 0.0005 :
 - continue the study with an increased total sample size N^* , so that CP with a total of N^* subjects is increased to 80%, same value as the (unconditional) desired power in the study design
 - N^* , however, is limited to 600 (which is twice the original sample size 300)
 - if $4\% \leq CP \leq 50\%$: continue the study without a change in sample size (otherwise, the sample size would need to be increased too much or the maximum sample size of 600 would not be sufficient to come close to a CP of 80%).

The table on the next page illustrated the proposed procedure for a number of possible results observed at the 2nd interim analysis.

Table with examples for the adaptive sample size procedure described above using the Cui/Hung/Wang (CHW) approach using a weighted (fixed weights determined by the stage-wise sample sizes planned at the design-stage) test for the final analysis:

2 nd IA results with n=150 subjects (50 for SOC, 100 for RESP301+SOC)		CP under observed trend for planned 300	Total sample size required for CP 80% under observed trend	CP under observed trend if total sample size capped by 600
15 (30%)	5 (5%)	$p < 0.0005 \rightarrow$ early stop for superior efficacy		
15 (30%)	10 (10%)	99%	Not applicable	Not applicable
15 (30%)	15 (15%)	90%	Not applicable	Not applicable
15 (30%)	18 (18%)	66%	393	Not applicable
15 (30%)	19 (19%)	55%	483	Not applicable
15 (30%)	21 (21%)	34%	[798]	[67%]
15 (30%)	26 (26%)	3.99%	Early stop for futility	
12 (24%)	10 (10%)	92%	Not applicable	Not applicable
12 (24%)	12 (12%)	77%	321	Not applicable
12 (24%)	14 (14%)	54%	498	Not applicable
12 (24%)	15 (15%)	42%	[646]	[77%]
12 (24%)	18 (18%)	14%	[1800]	[31%]
12 (24%)	20 (20%)	2.6%	Early stop for futility	
10 (20%)	8 (8%)	85%	Not applicable	Not applicable
10 (20%)	10 (10%)	64%	412	Not applicable
10 (20%)	11 (11%)	50.4%	534	Not applicable

10 (20%)	13 (13%)	26%	[1014]	[55%]
10 (20%)	15 (15%)	10%	[2460]	[23%]
10 (20%)	18 (18%)	1.4%	Early stop for futility	

Quantities in [] indicate theoretical values as sample size would not be increased per the currently proposed adaptive design.

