9.4.1 General Considerations

All statistical analyses will be conducted using SAS, Version 9.4 or later. Baseline characteristics will be summarized by treatment arm. For continuous measures the mean and standard deviation (SD) will be summarized. Categorical variables will be described by the proportion in each category. In addition, 95% confidence intervals (CIs) will be computed as indicated.

All the categorical variables including the primary endpoint will be summarized by treatment with the numbers and percentages of the participants. Treatment difference will be tested using a Cochran–Mantel–Haenszel test stratified by 1) country and 2) participant's clinical status at Baseline. For the categorical endpoints, relative risk and its 95% CI will be presented.

All of the continuous variables, including the changes from Baseline, will be summarized by treatment with the means, SD, medians and the ranges. The mixed model with repeated

measurements /analysis of covariance model with treatment, country, participant's clinical status at Baseline and visit as the model term, and Baseline value as the covariate will be used to test for the significance of the treatment difference. Least square means, standard errors, 95% CIs and p-values will be presented.

Time to event endpoints will be analyzed using the Cox Proportional Hazard model with treatment, participant's clinical status at Baseline and country as the model term. The hazard ratio of RESP301+SOC versus SOC will be presented along with 95% CI and p-value from the model. The Kaplan-Meier curves of the time to events will be presented by treatment for each applicable endpoint.

Handling of missing data

If participants are discharged from the hospital prior to Day 14 due to improvement of the clinical status and their status on Day 14 cannot be obtained, their status on Day 14 for the primary endpoint will be imputed with the status on the day of discharge. Depending on the reasons for missing data on the primary endpoint up to Day 14, additional sensitivity analyses will be performed. Further details on handling on missing data will be provided in the SAP.

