9.5 Interim Analyses

Two interim analyses will be performed.

1. The first analysis will be conducted when about 60 participants (40 participants in the RESP301+SOC arm and 20 participants in the SOC arm) have completed the Day 10 assessment. The purpose of this analysis is to evaluate efficacy of RESP301 with the application of a futility criterion based on the results on SpO₂ change from baseline on Day 10. The following futility criterion will be used for this first interim analysis:

If the difference in the percentage of participants with at least a 2% improvement in SpO₂ between both treatment arms is less than 5%, benefit of RESP301 treatment is not expected. For a final decision to stop the study for futility the results on other endpoints will be considered as well.

As no other modification of the study at the time of the first interim analysis is considered, no adjustment of the alpha level is required.

2. The second interim analysis will be conducted after 150 participants (100 participants in the RESP301+SOC arm and 50 participants in the SOC arm) have completed the Day 14 assessment. The purpose of this analysis is the assessment of futility or a sample size re-estimation in case the actual results differ from the original assumptions for the power calculations of the study, related to the percentage of participants meeting the primary endpoint in the control arm and/or the relative treatment benefit achieved in the RESP301+SOC arm compared to the SOC arm.

To account for the multiple testing due to the second interim analysis an adjustment for the type I error alpha will be applied using the Haybittle-Peto approach which would spend one sided alpha=0.0005 at the second interim analysis and leave one-sided nominal alpha of 0.0249 for the final analysis. The futility criterion for the second interim analysis will be based on the conditional power (CP) for the final results based on the assumption that the remainder of the study will follow the same trend as observed in the interim analysis. If CP at the time of the second interim analysis is less than 20% consideration

will be given to stop the study for futility. At the same time sample size re-estimation will be performed to achieve 80% power at the end of the study. The methodology for the adjustment and the procedure to maintain the type I error level will be described in greater detail in the SAP.

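### The conditional power and N* examples in Appendix 5 reproduce with an unpooled difference test, and the early-efficacy probabilities lie near that test, although the protocol plans a CMH test

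*Protocol*

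**What the plan says.** Section 9.4.1 fixes the test for categorical endpoints, including the primary one: "Treatment difference will be tested using a Cochran–Mantel–Haenszel test stratified by 1) country" and by clinical status at Baseline. Section 10.5.1 says the primary endpoint is "to be analyzed by a Cochran-Mantel-Haenszel (CMH) stratified for the factors used in the stratified randomization". Section 9.5 would "spend one sided alpha=0.0005 at the second interim analysis and leave one-sided nominal alpha of 0.0249 for the final analysis".

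Section 10.5.2 defines CP as the conditional probability of a significant result in favour of RESP301+SOC at the final analysis. Section 10.5.3 requires "calculation of conditional power (CP) given the interim results and calculated by assuming the interim estimates to be the true distribution parameters" for the rest of the study. It then sets the actions: stop for futility below 4%, no change from 4% to 50%, increase to N* (at most 600) between 50% and 80%, and stop for efficacy at one-sided p < 0.0005. A table of example interim results gives CP at 300 participants and the N* needed for 80% CP, using Cui/Hung/Wang fixed weights. Section 10.5.2 adds an early-efficacy stopping probability of 10% under 30% vs 15% and 28% under 30% vs 10%.

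No section names the statistic behind these figures or says that it differs from CMH. Section numbers are those of Amendment 1; version 1.0 prints the same tables in its section 10.6.

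**The concern.** If CP is the chance that the final test succeeds, it has to be computed for that test. CMH uses a variance pooled under the null hypothesis. With 2:1 allocation and the higher event rate expected in the smaller arm, the unpooled standard error is larger than the pooled one. CP computed with it is then lower, and N* higher, than for the planned test.

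The 50% and 80% cut-offs decide whether up to 300 further participants are recruited. The stopping probabilities tell the IDMC and the sponsor how likely an early efficacy stop is. If the printed figures belong to another test, they describe a different design from the one planned.

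**Working it through.** **Inputs.** Interim with 50 SOC and 100 RESP301+SOC, planned total 300, equal fixed weights (section 10.5.3). Final one-sided alpha 0.0249, z = 1.9617; interim 0.0005, z = 3.2905 (section 9.5).

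**Formulas.** Let p0 and p1 be the observed rates and p the overall rate.
- Unpooled SE = √[p0(1−p0)/50 + p1(1−p1)/100]
- CMH SE, single stratum = √[p(1−p)(1/50 + 1/100) × 150/149]
- z1 = (p0 − p1)/SE
- The final statistic is (z1 + z2)/√2, so success needs z1 + z2 > √2 × 1.9617 = 2.7742.
- Under the observed trend, z2 has mean z1√[(N−150)/150] and SD s. For the unpooled test s = 1; for CMH s = unpooled SE / CMH SE.
- CP at 300 = Φ[(2·z1 − 2.7742)/s]
- N* = 150 + 150·[(0.8416·s + 2.7742 − z1)/z1]²

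**Reproducing a printed row, 10 vs 11.** Unpooled SE = √(0.003200 + 0.000979) = 0.06465 and z1 = 0.09/0.06465 = 1.392. CP = Φ(0.010) = 50.4%, as stated. N* = 150 + 150 × (2.224/1.392)² ≈ 533; stated 534.

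**Same row with CMH.** p = 21/150 = 0.14, SE = √(0.14 × 0.86 × 0.03 × 150/149) = 0.06030, z1 = 1.493 and s = 0.06465/0.06030 = 1.072. CP = Φ(0.211/1.072) = 57.8% (58.3% if s is taken as 1). N* = 150 + 150 × (2.183/1.493)² ≈ 471.

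**Other rows** (events SOC vs RESP301+SOC; the CMH range runs from the actual s to s = 1; CMH N* uses the actual s):

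| Events | Stated CP, N* | Unpooled CP, N* | CMH CP | CMH N* |
|---|---|---|---|---|
| 15 vs 18 | 66%, 393 | 66.0%, 392 | 70-71% | 363 |
| 12 vs 12 | 77%, 321 | 76.6%, 321 | 82-84% | no increase |
| 12 vs 14 | 54%, 498 | 53.9%, 496 | 60% | 449 |
| 10 vs 10 | 64%, 412 | 63.7%, 409 | 71-73% | 358 |
| 10 vs 11 | 50.4%, 534 | 50.4%, 533 | 58% | 471 |
| 15 vs 26 | 3.99%, stop | 3.99% | 4.1-4.2% | n/a |
| 12 vs 20 | 2.6%, stop | 4.7% | 4.9-5.2% | n/a |

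Over all 18 printed CP values, the unpooled test is within 2 points for 17, and CMH with s = 1 for 5. Continuity-corrected pooled, log odds ratio, log relative risk and arcsine statistics match only 5 to 7. The row 12 vs 20 fits neither test; 2.6% is the value for 21 events.

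**Early-efficacy stop**, exact binomial enumeration of 50 and 100 participants at one-sided p < 0.0005:

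| True rates | Stated | Unpooled | CMH |
|---|---|---|---|
| 30% vs 15% | 10% | 9.0% | 14.2% |
| 30% vs 10% | 28% | 29.7% | 43.1% |

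Simulated stratified CMH with 1 to 9 equal strata gives 14% and 42-43%.

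**Effect on decisions.** Under 30% vs 15%, about 10.5% of interim outcomes fall in a different zone with CMH (s = 1): 3.8% move from increase to no increase, 1.5% from no change to increase, and 5.2% from continuing to an efficacy stop. Changes from futility stop to continuing make up 0.02%.

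**The case against.** The strongest reply is that the table only illustrates a proposal with fictitious data, and that section 9.5 leaves the re-estimation method to the SAP and the DMC Charter. This stands in part. A reader might infer that the second interim will in fact act on a CP that is too low. The protocol does not say so: the unpooled statistic is inferred from the printed numbers, and the interim may well be run with CMH. But then the printed examples and stopping probabilities do not describe that interim. The mismatch remains either way.

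A second reply is that the match is not perfect. That is also true: the row 12 vs 20 fits neither test, and the stopping probabilities are near the unpooled values, not equal to them. Neither point brings CMH closer.

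A reader might also infer that futility recommendations would flip, because 15 vs 26 moves from 3.99% to just over 4%. This carries no weight. Futility is non-binding, the stated 70% and 6% futility probabilities reproduce under both tests, and the row falls back below 4% when the interim CMH is spread over six or nine equal strata (s = 1).

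Nor is inflation of the trial's type I error shown. The Cui/Hung/Wang weights are fixed in advance. In the decision zone an unpooled CP above 50% implies a CMH CP above 50%, so the condition cited for the unweighted alternative also holds.

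**Conclusion.** The point holds as a mismatch between the planned test and the printed figures. In the middle of the CP range the examples are about 3 to 9 points below the CMH values. N* in the four increase rows recomputed above is too high by about 30 to 63 participants (393 − 363 = 30 and 534 − 471 = 63), and one printed increase, 12 vs 12, would not be triggered. The early-efficacy probabilities understate the planned test: 10% against about 14%, and 28% against about 43%. The futility end is essentially unaffected.

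The CMH values assume a single stratum and normal approximations for CP. Splitting the interim sample into three to nine equal strata with events in proportion lowers CP somewhat (s = 1): 12 vs 12 to 83-81% and 10 vs 11 to 58-55%. The direction holds, but with many strata 12 vs 12 comes close to the 80% line. The number of strata is an assumption, since the protocol does not give the number of countries.

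**What to change.** State in section 10.5.3 that the interim p-value, CP, N* and the final test all use the same stratified CMH statistic. Recompute the tables in sections 10.5.2 and 10.5.3 for it, by simulation or with the correct stage-2 variance. Putting a CMH z1 into the formula with s = 1 makes N* too small (for 10 vs 11, about 454 instead of 471). The strata have to be settled first, because section 9.4.1 names clinical status at Baseline where section 10.5.1 refers to the randomization factors. Correct the row 12 vs 20 separately.

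The cost is a rerun of the design calculations and some wording. A reader might infer that the change can only save participants, and that is not so. N* falls in the increase rows, but a small share of outcomes moves from no change into the enlargement zone: 11 vs 13 (CP 45.6% to 52%, total 300 to about 532), 14 vs 18 (46.8% to 51%, about 534) and 8 vs 8 (48% to 58%, about 477).
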